4.1 Inclusion Criteria

- People with haemophilia A and an inhibitor aged >8 yrs who are prescribed emicizumab therapy in routine clinical practice.
- Parents and siblings of children aged <16 years with haemophilia A who are prescribed emicizumab.

- Partners/carers/siblings/children of adults with haemophilia A who are prescribed emicizumab will become patient 'dyads'
- Those who have given written consent to be in the study.

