An Exploration of the Impact of Emicizumab on the Lives of People with Haemophilia and Inhibitors and their Families

Principal investigators: [name]

Co-Investigators: [name], [name]

Study Sponsor: Haemnet (Registered Charity No 1152241)

Study Coordinator: [name], Haemnet

Version date: 4 November 2019

Version number: Version 4

CONFIDENTIAL

Information and data included in this document contain privileged or confidential information, which is the property of the sponsor. No person is authorised to make it public without written permission of the sponsor. These restrictions on disclosure will apply equally to all future information supplied to you, which is indicated as privileged or confidential. This material may be disclosed to and used by your staff and associates as may be necessary to conduct the clinical study.

List of Abbreviations

| Abbreviation | Definition |
|--------------|--|
| CCC | Comprehensive Care Centre |
| EAMS | Early Access to Medicines Scheme |
| Emi | Emicizumab |
| Haemo-QOL | Haemophilia Quality of Life scale |
| Hep-Test-Q | Haemophilia and Exercise Project Test Questionnaire |
| HJHS | Haemophilia Joint Health Score |
| HRQoL | Health-Related Quality of Life |
| HTC | Haemophilia Treatment Centre |
| PWH | People with Haemophilia |
| QoL | Quality of Life |
| SO-FIT | Study Of physical Function In adolescenTs with haemophilia |

Study Synopsis

| | |
|---------------------------------|--|
| Title | Emi and Me: an exploration of the impact of emicizumab on the lives of people with haemophilia and inhibitors and their families |
| Short Title | Emi and Me |
| Study aim | This study aims to examine the real-life experience and impact of using emicizumab in a cohort of patients with haemophilia and inhibitors, who are being prescribed emicizumab in routine clinical practice as well as those who have been in the clinical trials. We also intend to capture the impact of emicizumab use on the lives of close family members (parents/carers/children/siblings). |
| Primary Objective | To capture the real-life experience of using emicizumab for haemophilia inhibitor therapy for the patient with haemophilia and his close family members |

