| Secondary Objectives | To describe difference patient satisfaction with injections (numbers of injections, how to remember treatment dates, and so on). To understand user's expectations of emicizumab and how they see future haemophilia care (less frequent injections, impact on home storage, number of bleeds, reduced hospitalisations and so on). To describe the as yet 'unseen' impact on the extended family – and to seek their views of innovative therapy for haemophilia. |
| Design | Non-interventional qualitative study |
| Number of Centres | N/A (recruitment via social media) |
| Duration | 6 months data collection 12 months total study duration |
| Number of Subjects | 25 'dyad' pairs |
| Inclusion Criteria | Study participants will be people with inhibitors using emicizumab (prescribed by treating clinicians) in usual clinical care. Family members of participants will also be included. |
| Exclusion Criteria | Participants will be excluded from the study if they do not have an inhibitor, are not being treated with emicizumab, do not speak English (for the interviews) or do not consent. |
| Statistical Analysis | This is a qualitative study using established qualitative research methodologies (grounded theory). Statistical evaluation is not appropriate |
| Operational procedures | |
| Ethical approval | NHS ethical approval will be sought from HRA |
| Data analysis | To be conducted by Haemnet |
| Write up and publication | Lead researcher and research team |

Emi and Me

An Exploration of the Impact of Emicizumab on the Lives of People with Haemophilia and Inhibitors and their Families

Index

| | | |
|---|--|------------------------------|
| 1 | Background | 5 |
| 1.1 | Disease Introduction | 5 |
| 1.2 | Rationale for the study..... | 6 |
| 2 | Aim and Objectives | 6 |
| 2.1 | Aim | 6 |
| 2.2 | Primary Objective..... | 6 |
| 2.3 | Secondary Objectives | 7 |
| 3 | Study design | 7 |
| 3.1 | General Design | 7 |
| 3.2 | Primary Endpoints..... | 7 |
| 3.3 | Secondary endpoints..... | 7 |
| 3.4 | Statistical analysis and sample size calculation..... | 8 |
| 4 | Study Group | 8 |
| 4.1 | Inclusion Criteria..... | 8 |
| 4.2 | Exclusion Criteria | 9 |
| 5 | Recruitment, Screening and Study Procedures | 9 |
| 5.1 | Study visits 1 (inclusion) | 9 |
| 5.2 | Study duration..... | 10 |
| 5.3 | Safety reporting..... | 10 |
| 6 | Data analysis plan | 10 |
| 6.1 | Data analysis..... | 10 |
| 7 | Ethics..... | 11 |
| 7.1 | Informed consent..... | 11 |

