1.2 Rationale for the study

Emicizumab offers patients protection from bleeding with fewer injections, this should reduce treatment burden. While patient expectation is high (as evidenced by the conversations on UK haemophilia social media sites) there are risks that patients may forget to treat and thus experience bleeds. During clinical trials participants have been monitored closely and, through questionnaire completion, have described improvement in quality of life [Mancuso et al, 2018, Oldenburg et al 2019].

What is also apparent to clinical teams is the dramatic change to life experience of not just the patient but his family – the ability to travel, to plan attending events knowing that bleeds will not occur, even potentially to have another child because of the reduction in treatment burden, particularly the time needed for treatment and rehabilitation.

This therapy represents a substantial shift in the entire life experience of living with and managing haemophilia with inhibitors. As such, there is a need to look beyond the quantitative data collected in clinical trials and to assess the real impact of therapy on the everyday lives of patients and their families, gathered using qualitative research techniques.

Emicizumab has been available in the UK in clinical trials and as part of an Early Access to Medicines Scheme (EAMS) for non-trial eligible patients since spring 2018. It was recently licensed in the UK and is now available for routine clinical care for any person with haemophilia A and an inhibitor.

We hypothesise that patients and their carers/families will be excited about this new treatment option and that for most, if not all, the promise of improved care and quality of life will be a reality.

2 Aim and Objectives

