2.1 Aim

This study aims to examine the real-life experience and impact of using emicizumab in a cohort of patients with haemophilia and inhibitors, who are being prescribed emicizumab in routine clinical care or as part of the EAMS process as well as those who have been in the clinical trials. We also intend to capture the impact of emicizumab use on the lives of close family members (parents/carers/children/siblings). Each participant and his family members will be deemed a study 'dyad'.

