3.1 General Design

This is a prospective, observational cohort qualitative research study to be conducted among patients using emicizumab in routine clinical practice.

The study is designed to allow English-speaking patients and their families to tell their own life stories through narrative accounts. The narratives represent a true sharing of experiences valued by the tellers, listeners and gatherers [Hardy et al, 2009], and therefore offer insight into how these patients and families cope with haemophilia.

Most experienced practitioners familiar with haemophilia have preconceived ideas and theories that may potentially bias data capture. Grounded theory is a research methodology that allows identification and description of the broad spectrum of life with haemophilia from the perspectives of the patient and their families. This methodology enables rich data capture across a large age range and allows for deep consideration of data, allowing research questions to be re-shaped as evolving themes and new concepts emerge.

The study will form part of a PhD by published works undertaken by the PI and supervised by [name].

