We estimate that in the UK, around 20 patients have been treated with emicizumab in clinical trials (principally in the major London centres). Around 40 people received therapy with emicizumab as part of the Early Access to Medicines Scheme (EAMS) for non-clinical trial eligible patients. Another small cohort of people have received emicizumab since it was licensed in the UK in May 2018.

From this sub-population of <100 people, we would hope to recruit around 25 to the study, together with at least one family member.

Prescribed doses and frequency of treatment will be decided and prescribed by the patient's clinical team. No patient will switch to emicizumab to gain entry to this study.

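### Does the inclusion criterion in section 4.1 shut out people supplied through EAMS, whom the aim in section 2.1 names?

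*Protocol*

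**What the plan says.** The patient criterion in Protocol section 4.1 reads "People with haemophilia A and an inhibitor aged >8 yrs who are prescribed emicizumab therapy in routine clinical practice". The family-member criteria in the same section ask only that the patient be prescribed emicizumab.

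The aim in section 2.1 is wider. It covers patients "who are being prescribed emicizumab in routine clinical care or as part of the EAMS process", and adds people who have been in the clinical trials. The Study aim row of the synopsis drops EAMS: "who are being prescribed emicizumab in routine clinical practice as well as those who have been in the clinical trials".

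Two other places describe the population without naming EAMS. The synopsis inclusion row says "Study participants will be people with inhibitors using emicizumab (prescribed by treating clinicians) in usual clinical care", and section 3.1 says the study is "to be conducted among patients using emicizumab in routine clinical practice".

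Section 4 builds the recruitment pool from about 20 trial patients, about 40 EAMS patients ("Around 40 people received therapy with emicizumab as part of the Early Access to Medicines Scheme (EAMS") and a small group treated since licensing. It puts the total below 100 and hopes to recruit about 25.

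**The concern.** Eligibility criteria decide who is enrolled, so they should describe the population that the aim describes. Here the aim names a supply route that the criterion does not. The protocol also seems to treat the two routes as distinct. Section 2.1 joins them with an *or*. Section 1.2 first describes access "as part of an Early Access to Medicines Scheme (EAMS) for non-trial eligible patients since spring 2018" and then says separately "It was recently licensed in the UK and is now available for routine clinical care". No sentence says that EAMS supply counts as routine practice.

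A nurse who applied 4.1 to the letter could turn away a patient still on EAMS. With about 40 of fewer than 100 people ever treated that way, a strict reading might seem to remove a large part of a small pool and leave a report whose population does not match its aim.

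**Working it through.** The protocol has no sample-size formula; the target of about 25 is a hoped-for number. The check is therefore a comparison of texts plus simple arithmetic on the recruitment pool.

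**Step 1. Set the texts side by side.**

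| Place in the Protocol | Supply route |
|---|---|
| Synopsis, Study aim | routine practice, plus people who have been in trials |
| Synopsis, Inclusion Criteria | usual care, explained as prescribing by treating clinicians |
| Section 2.1 | routine care or EAMS, plus people who have been in trials |
| Section 3.1 | routine practice |
| Section 4 | trial, EAMS and post-licence patients all counted in the pool |
| Section 4.1, patient criterion | routine practice |
| Section 4.1, family criteria | no route stated |
| Section 5, recruitment | patients prescribed emicizumab and seen at the centres for direct care; no route filter |

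The exclusions legible in section 4.2 and those in the synopsis do not mention supply route. The mismatch is therefore real, but the pool in section 4 and the recruitment route in section 5 both take EAMS patients in.

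**Step 2. Who could be affected?** Criterion 4.1 tests current prescribing. A former EAMS patient now on routine supply meets it, as does a former trial patient now on routine supply. That leaves only people still supplied through EAMS.

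- Upper limit: about 40, if nobody ever treated through EAMS has moved to routine supply.
- Lower limit: 0, if all have moved.

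The documents do not give the number in between. Three statements point to the low end. Section 4 puts EAMS treatment in the past tense. Section 1.2 says that routine supply is now open to any person with haemophilia A and an inhibitor. Section 4 dates the licence to May 2018, and this version is dated 4 November 2019:

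- from 1 May 2018: 18.1 months;
- from 31 May 2018: 17.1 months.

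**Step 3. What would the extreme case do to recruitment?**

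- Trial plus EAMS patients: 20 + 40 = about 60, so the post-licence group is below 100 − 60 = 40.
- Whole pool: 25 patients are more than 25/100 = 25% of it.
- Pool without any EAMS patient: fewer than 100 − 40 = 60 remain, and 25 patients are more than 25/60 = 42% of them.

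The second share applies only if all of the roughly 40 are still on EAMS and 4.1 is read strictly. Nothing in the protocol supports that combination. At the lower limit the share stays at just over 25%.

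**Step 4. Would the analysis change?** Section 3.3 plans to compare children and siblings, carers, and adult and child patients. Section 3.4 gives patients versus parents as an example, with age, regimen, bleeds and joint health as possible explanatory factors. Supply route is in neither list, and interviewing continues to data saturation. No named result depends on whether a patient's drug comes through EAMS or routine supply.

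**The case for a change.** The best case for a change is that the text should be settled either way. Section 2.1 uses the present tense for EAMS prescribing. If people remain on EAMS, 4.1 read literally excludes patients whom the aim names; if nobody does, 2.1 names a route no longer in use. The *or* in 2.1 and the three separately counted groups in section 4 suggest that the authors saw EAMS as distinct from routine care. The correction would be one clause and would need no extra participants or procedures.

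Part of this stands. The passages do differ, and the two statements of the aim differ from each other. But naming the routes separately in one place does not show that 4.1 was meant to exclude one of them. In a non-interventional study, routine practice is most naturally set against prescribing driven by the study: section 4 leaves dose and frequency to the patient's clinical team and says that nobody will switch to emicizumab to gain entry. The synopsis inclusion row points the same way when it explains usual care as prescribing by treating clinicians.

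It also goes too far to say that the report could not describe one population. If nobody is still on EAMS, both texts cover the same people. If some are, describing them as patients prescribed emicizumab by their treating clinicians covers both routes.

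**Conclusion.** The wording mismatch exists, but it is clerical and calls for no change to the plan. It could touch only people still on EAMS supply at version 4. That number is not given, lies between 0 and about 40, and may well be 0. No recruitment shortfall and no effect on the findings is shown.

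This rests on two assumptions: that centre staff read the criterion as section 4 and the synopsis inclusion row suggest, and that most or all EAMS patients had moved to routine supply by November 2019. The second is an inference from tense and dates, not a stated fact. The point would carry more weight only if a sizeable share of the roughly 40 were still on EAMS and centres turned them away.

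If the protocol is amended for another reason, one common description of the population would tidy the text. The age limit in the same criterion, against the any-age description in section 4, is a separate matter and is not settled here.

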4.2 Exclusion Criteria

[figure not shown]
- Patients prescribed treatment other than emicizumab for their haemophilia
- Non-English speakers
- Those who do not consent to be in the study.

5 Recruitment, Screening and Study Procedures

The study will be advertised via Haemnet to nurses in haemophilia centres where patients who are being prescribed emicizumab will be seen for direct clinical care. Once identified potential participants will be given information about the study by their clinical team and will be invited to participate. If they agree to participate they will be contacted by the research team to organize a mutually convenient time for their interview which could be undertaken at hospital, home or other mutually convenient site. The Haemnet lone worker policy (appendix 2) will be followed to ensure interviewer safety.

5.1 Study visits 1 (inclusion)

There will be a single study visit, at which all study data will be collected. This is summarised in the panel.

5.2 Study duration

The study will last for 6 months, during which time each dyad will be interviewed once only.

5.3 Safety reporting

Emicizumab is a newly licensed therapeutic option for people with haemophilia as such safety data is still being collected.

Although adverse event information is not being actively solicited via this protocol, physician/consumers are reminded to report any adverse reactions (for which they suspect a causal role of a medicinal product) (see Appendix 3) that come to their attention either to the marketing authorization holder of the suspected medicinal product, via the Roche Adverse Event and Special Situation Reporting Form to be supplied to the physician (for Roche medicinal products) (see Appendix 4), or to the concerned competent authorities via the national spontaneous reporting system.

In addition, the following should also be reported if occurring during exposure to a marketed medicinal product, even in the absence of adverse events:

- Pregnancy
- Breastfeeding
- Abnormal laboratory findings
- Overdose, abuse, misuse, off-label use, medication error or occupational exposure
- Reports of lack of efficacy
- Product quality defects and falsified medicinal products
- Data related to a suspected transmission of an infectious agent via a medicinal product
- Drug interactions (including drug/drug, drug/food, drug/device and drug/alcohol)

When a subject is not exposed to a marketed medicinal product, but the physician/consumer becomes aware of the potential for a medication error, or an intercepted medication error, this should also be reported.

If during one of the interviews a participant mentions an adverse event, or any of the special situations described above, the interview will continue without interruption. Once the interview is complete, an appropriate adverse event report will be prepared and submitted.

6 Data analysis plan

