1.1 Disease Introduction

Haemophilia A is a rare congenital disorder caused by an inherited genetic defect of the X chromosome that results in a deficiency in factor VIII production. Factor VIII plays a pivotal role in the coagulation cascade, bringing together the clotting factors IXa and X, a critical step in the formation of a blood clot to help stop bleeding. Haemophilia A results in impaired clot formation and can lead to uncontrolled and often spontaneous bleeding. It affects approximately one in every 5,000 males [Srivastava et al, 2013]. Different types of severity are recognised:

- “severe” (factor activity is less than 1%)
- “moderate” (factor activity is 1-5%)
- “mild” (factor activity is 6-25%).

In its severe form, haemophilia results in recurrent joint and muscle bleeds that predispose to arthropathy, muscle contracture and disability. Treatment of affected individuals in the UK is with FVIII prophylaxis, which decreases spontaneous bleeding events and resultant joint damage [Richards et al, 2010]. Prophylaxis requires frequent intravenous infusions, which can be as often as daily but are usually 2-3 times per week.

A serious complication of treatment is the development of inhibitors to infused factor VIII replacement therapies. Inhibitors are antibodies developed by the body's immune system that bind to and block the efficacy of replacement factor VIII, making it difficult, if not impossible to obtain a level of factor VIII sufficient to control bleeding. Up to 40% of patients receiving replacement factor develop inhibitors [Iorio et al, 2017].

Of these patients, who are predominantly children, between 50 and 86% can be tolerised through extended periods of very high treatment [Holstein et al, 2016]. Unfortunately, for a small number of these children, this treatment fails leaving a cohort of young children/adolescents who join a group of adults who never had access to this treatment [Khair et al, 2018]. For this ever-growing cohort of individuals treatment is with bypassing agent therapy either when bleed occur (on-demand or episodic therapy) or as prophylaxis [Dekoven et al, 2013].

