Treatment of inhibitors is burdensome for the patient and his family [Lindvall et al, 2014; DeKoven et al, 2014] as it requires repeated intravenous infusions. Furthermore, treatment does not always alleviate bleeding, which can result in haemophiliac arthropathy, reduced mobility and pain and frequent episodes of hospital delivered care [Berntorp et al, 2011].

Emicizumab is a bispecific factor IXa- and factor X-directed humanised monoclonal antibody that has been co-developed by Chugai, Roche and Genentech. It has been designed to mimic the activity of factor VIII bringing together factor IXa and factor X, proteins that are required to activate the natural coagulation cascade and restore the blood clotting process for haemophilia A patients. Emicizumab is a prophylactic (preventative) treatment that can be administered by an injection of a ready-to-use solution under the skin (subcutaneously) once weekly or potentially once monthly following initial weekly ‘loading’ doses [Shima et al, 2016]. In a pivotal phase III study, which compared emicizumab with on-demand (no prophylaxis) and prophylaxis use of bypassing agents (BPAs) in adults and adolescents with haemophilia A with inhibitors, the primary endpoint showed a clinically meaningful and statistically significant reduction in treated bleeds of 87% (risk rate [RR]=0.13, p<0.0001) with emicizumab prophylaxis [Oldenburg et al, 2017]. Furthermore, over a median observation time of 31 weeks, substantially more patients experienced zero bleeds with emicizumab prophylaxis.

Consequently, patient expectation of emicizumab is significant. On haemophilia-specific social media websites, many patients have expressed optimism for a treatment likely to result in reduced treatment burden and fewer bleeds, with a consequent impact on mobility and pain. Treatment burden also includes the time commitment required for treatment, which is reported to impact on treatment adherence [Thornburg, 2018]. The frequency of infusion of current therapy is often cited as influencing adherence to treatment; decreased frequency of infusions and sub-cutaneous administration may encourage adherence and better treatment outcomes [Hacker et al, 2001].

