6.1 Data analysis

This study will be analysed using grounded theory. Grounded theory involves gathering rich data, using a variety of methods, including interviews, ethnography and textual analysis identifying themes, coding and analysing these finally developing theories about the data that has emerged [Charmaz, 2006]. Grounded theory has been used extensively in research with children and families [Neill, 2007].

Taped Interviews:

- The interviews will be transcribed and anonymised during the transcription process.
- Once the interviews are transcribed, the text will be read and re-read whilst listening to the recordings to ensure correct transcription. Following this review process and analysis the tapes will be destroyed and the transcripts will become the source data
- The interviews will be coded into themes by the whole research team, the themes will then be analysed further using a transformational framework, identifying overarching themes or concepts, summarising and synthesising the data and using descriptive analysis to represent the findings/dyads views [Spencer et al, 2003].
- A table of the themes will be produced
- These themes will characterise recurring ideas and thoughts from the participants and will form the basis for further analysis and publications.
- Individual quotes may be used – these will be anonymised, this will be in the information sheet(s) and consent.

Field notes:

- Immediately after the interview, the researcher will record any thoughts, reflections or observations made during the interview. In particular any thoughts/ideas about emerging themes will be recorded.
- These notes will be analysed as part of the framework analysis [Ritchie et al, 2003].

7 Ethics

There is minimal risk to participants or researchers from this study. Participants will be invited to one interview to discuss their hopes, fears, expectations and the realities of the new treatment.

In the event that any patient or family member becomes distressed by this they will be referred (with consent) to the psychology services affiliated with the haemophilia centres from which they have been recruited.

National guidance on interviewing children [MRC, 2004; RCPCH, 2000] will be followed.

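### Section 5.3 tells the interviewer to carry on after any adverse event is mentioned, with no exception for a current event needing prompt care and no route back to the haemophilia centre

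*Protocol*

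**What the plan says.** The last paragraph of Section 5.3 (Safety reporting) applies when a participant mentions, during an interview, an adverse event or any of the special situations listed above it. The instruction is that "the interview will continue without interruption. Once the interview is complete, an appropriate adverse event report will be prepared and submitted". It is not limited by seriousness, by timing, or by whether the event is still going on.

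Earlier in the same section, physicians and consumers are reminded to report suspected reactions to the marketing authorisation holder or to the competent authorities. The physician appears there as a reporter who is supplied with a form.

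The protocol has one referral route for participants, in Section 7 (Ethics). Someone distressed by the interview is covered as follows: "they will be referred (with consent) to the psychology services affiliated with the haemophilia centres from which they have been recruited".

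Section 5 says of the interview: "which could be undertaken at hospital, home or other mutually convenient site". Section 7.5 has a patient representative helping to conduct the patient interviews. Section 5.2 says "each dyad will be interviewed once only".

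**The concern.** The rule is right for most of what it covers. It gives the wrong direction in the one case where time matters: the participant describes something happening now that the centre is not managing. Read literally, the interviewer finishes the interview, files a pharmacovigilance report and has no further step to take.

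The protocol itself explains why this matters in this population. Section 1.1 says that inhibitors block infused factor VIII, "making it difficult, if not impossible to obtain a level of factor VIII sufficient to control bleeding". It adds that in patients with inhibitors "treatment does not always alleviate bleeding, which can result in haemophiliac arthropathy, reduced mobility and pain and frequent episodes of hospital delivered care". Section 1.2 says of emicizumab users that "there are risks that patients may forget to treat and thus experience bleeds". Patients may be children (Section 4.1 admits those over 8 years), the setting may be a private home, and nothing in the text available to me says that a clinician attends every interview. With a single interview per dyad, no later study contact exists at which the event could be picked up.

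What is at stake is the safety of an individual participant. The themes, endpoints and analysis are unaffected.

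**Working it through.** The protocol states no figure on this point, so the check is a reading of the rule against every other place that could supply an exception or a route to care.

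**Step 1. Does a current bleed fall under the rule?** Yes. The Safety Reporting Definitions appendix defines an adverse event broadly, as any untoward medical occurrence, and includes worsening of an existing condition. Section 5.3 also lists reports of lack of efficacy among the special situations, which could include a breakthrough bleed.

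**Step 2. Does anything shown provide an exception or a clinical step?**

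| Place in the protocol | What it provides | Pause for an urgent event? | Direction to the centre? |
|---|---|---|---|
| 5.3, reporting paragraph | Two recipients: marketing authorisation holder, competent authorities | No | No |
| 5.3, last paragraph | Continue, then report | No | No |
| 7 Ethics | Consented referral to psychology services, for distress | No | For distress only |
| 7.1 Informed consent | Withdrawal at any stage | No; the choice is the participant's | No |
| Lone Worker Policy appendix | Aimed at staff safety, with a general duty of care to others | No | No |
| Safety Reporting Definitions appendix | Definition of an adverse event; causality assessment by the PI | No | No |
| Reporting form, instructions | Form goes to the manufacturer's safety unit | No | No |
| Reporting form, section 2 | Permission to contact the healthcare professional about the event | No | A field that serves the report, completed after the interview |

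No row supplies either element for a medical event.

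**Step 3. How many interviews does the rule govern?**

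- Treated patients: about 25. Section 4 says "we would hope to recruit around 25 to the study, together with at least one family member".
- Interviews per dyad: 1 (Section 5.2).
- 25 × 1 = about 25 interviews involving a treated patient.
- Report recipients named in 5.3: 2. Treating centre among them: 0.

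The 25 is the number of interviews to which the rule applies, not the number expected to involve an urgent event. The protocol gives no rate from which that second number could be derived.

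**The case against.** The strongest reply is that Section 5.3 is pharmacovigilance text. Its last paragraph fixes when a report is made, after the interview and not during it, and does not set out to govern clinical care. Care belongs to the patient's own team throughout, in a non-interventional study that does not solicit adverse events. Nothing forbids an interviewer from telling a patient to ring the centre. The interview is at a mutually convenient time, so a patient with an acute bleed can postpone or stop it.

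Two further points have force. The two Section 1.1 statements describe infused factor VIII and inhibitor treatment before emicizumab is introduced, whereas this cohort is on emicizumab, for which the same section reports an 87% reduction in treated bleeds. And the panel in 5.1, the interview guide, the information sheets and some of the study personnel pages were not available to me, so an escalation step could sit in one of them.

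Much of this stands as a limit on size. The bleed reduction and the continuing care by the centre make the event uncommon, and past or already managed events are unaffected. None of it removes the problem. The sentence does govern the interview as well as the report, because it says that the interview is not to be interrupted. An interviewer who stops for an active bleed acts sensibly but departs from the written rule. Section 5.3 makes no cross-reference to any escalation step elsewhere. The 87% reduction is not elimination, and Section 1.2 itself expects bleeds after forgotten doses. These patients still have an inhibitor, so the Section 1.1 statement about factor VIII remains relevant if they bleed.

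**Conclusion.** The concern holds as a minor participant-safety point. Section 5.3 states a universal rule to continue and then report. It has no exception for a current event that appears to need prompt attention and no direction back to the haemophilia centre, and no other text shown supplies either. The rule governs about 25 interviews with treated patients. The harmful case is confined to a current event that the centre is not already managing. It is expected to be uncommon, and I put no probability on it.

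The conclusion rests on the text available. An instruction in the interview guide, the 5.1 panel or the information sheets would reduce the practical risk, but 5.3 would still need to say so or point to it.

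**What to change.** Add to the last paragraph of Section 5.3 wording such as:

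> *If a participant describes a current event that appears to need prompt medical attention (for example an untreated bleed), the interview is paused and the patient or parent is advised to contact the haemophilia centre or emergency services at once; with consent, the interviewer informs the centre. For other adverse events the interview continues, and afterwards the patient or parent is advised to tell the centre if it is not already aware, in addition to the report.*

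Add one matching line to the information sheet. Leave missed doses and the other special situations on the existing reporting route, so that participants can still speak freely about adherence without it being passed to the prescriber.

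The cost is two sentences, one information-sheet line and an occasional interrupted interview. The centre learns of an event from the interviewer only with consent, and no endpoint or analysis changes.
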